Objectives:	
Primary: To assess the safety and tolerability of Lactobacillus reuteri (Lr) strain DSM 17938 in healthy infants and children. Safety will be assessed through the evaluation of adverse effects in both study arms for 90 days following product administration and by laboratory monitoring of CBC, AST, ALT, T. bilirubin, BUN and creatinine prior to product or placebo administration with follow-up assessment at 5 and 28 days. Tolerability will be assessed based on parental report of subjective symptoms of well-being during product administration and thru D28 of the study.
 
Secondary: To evaluate the duration of shedding of Lactobacillus reuteri (Lr) strain DSM 17938 following administration. This will be determined by and endpoint PCR assay for L. reuteri done on stool collected on D3, D5, D12, D15, D18, D24, D28, D36 on all participants.

Population:	The sample size of sixty is expected to include an equal number of healthy boys and girls 2-24 months of age at the time of enrollment from a rural community in Loreto Peru where chronic undernutrition and diarrheal disease are both highly prevalent.
Phase:	I
Number of Sites:	Single site- Loreto, Peru
Study Duration:	7 months
Subject Participation Duration:	3 months
Description of Agent or Intervention:	
1. Active Product: Description Lactobacillus reuteri 17938 suspended in sunflower oil, medium chain triglyceride oil, silicone dioxide. Total viable count of L. reuteri 17938 1×10^8 CFU/5 drops per day for 5 consecutive days
 
2. Placebo: Composition Sunflower oil, medium chain triglyceride oil and silicon dioxide. Total viable count of L. reuteri is zero CFU/ 5 drops.

Estimated Time to Complete Enrollment:	4 months

Schematic of Study Design:

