9.2 Methods and Timing for Assessing, Recording, and Analyzing Safety Parameters

9.2.1 Adverse Events

Adverse Event: ICH E6 defines an AE as any untoward medical occurrence in a patient or clinical investigation subject administered a pharmaceutical product regardless of its causal relationship to the study treatment. An AE can therefore be any unfavorable and unintended sign (including an abnormal laboratory finding), symptom, or disease temporally associated with the use of study product including active or placebo.

1
2 According to the U.S. DHHS Common Rule an AE **does** include any:

3
4

- exacerbation of a pre-existing illness, such as asthma.
- increase in frequency or intensity of a pre-existing episodic event or condition.
- condition detected or diagnosed after study product administration even though it may have been present prior to the start of the study.
- continuous persistent disease or symptoms present at baseline that worsen following the start of the study.
- symptoms associated with disease not previously reported by the subject will be recorded as an AE.

12
13 According to the U.S. DHHS Common Rule

14 (<http://www.hhs.gov/ohrp/policy/advevntguid.html>) an AE **does not** include a/an:

15

- medical or surgical procedure (eg, surgery, circumcision, transfusion); the condition that leads to the procedure is an AE.
- pre-existing diseases or conditions present or detected at the start of the study that do not worsen.
- situations where an untoward medical occurrence has not occurred (eg, hospitalization for elective surgery, social and/or convenience admissions).

21
22 All AEs including local and systemic reactions not meeting the criteria for “serious
23 adverse events” (See Section 9.2.2) will be captured on the ADVERSE EVENT CRF.
24 Information to be collected includes event description, time of onset, clinician’s (MD)
25 assessment of severity, relationship to study product and time of
26 resolution/stabilization of the event. All AEs occurring while on study product or within
27 90 days of follow-up must be documented appropriately regardless of relationship to the
28 study product. All AEs will be followed to adequate resolution.

29
30 Any medical condition that is present at the time that the subject is screened will be
31 considered as baseline and not reported as an AE. However, if it deteriorates at any
32 time during the study, it will be recorded as an AE.

33

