32 **Relationship to Study Products:** AEs will be assessed for relationship to study product.
33 The clinician's assessment of an AE's relationship to test article (study drug) is part of
34 the documentation process, but it is not a factor in determining what is or is not reported
35 in the study. If there is any doubt as to whether a clinical observation is an AE, the event
36 will be reported. All AEs must have their relationship to study product assessed using
37 the terms: associated or not associated.

38
39 In a clinical trial, the study product must always be suspect. To help assess, the
40 following guidelines will be used.

41 • **Associated** – The event is temporally related to the administration of the study

1 product and no other etiology explains the event.

2 • **Not Associated** – The event is temporally independent of study product and/or the
3 event appears to be explained by another etiology.

4

5

6 9.2.2 Serious Adverse Events (SAE)

7

8 **Definition of a Serious Adverse Experience (SAE):**

9 Serious adverse event (SAE): A Serious Adverse Event is defined as an AE meeting one
10 of the following conditions

11

12 • Death during the 3 month period of protocol defined surveillance

13

14 • Life Threatening Event (defined as a subject at immediate risk of death at the time
15 of the event)

16

17 • An event requiring inpatient hospitalization or prolongation of existing
18 hospitalization during the period of protocol defined surveillance

19

20 • Results in persistent or significant disability/incapacity

21

22 • Any episode of bacteremia due to *Lactobacillus reuteri*, the study probiotic

23

24 • Any other important medical event that may not result in death, be life threatening,
25 or require hospitalization, may be considered a serious adverse experience when,
26 based upon appropriate medical judgment, the event may jeopardize the subject
27 and may require medical or surgical intervention to prevent one of the outcomes
28 listed above. Examples of such medical events include allergic bronchospasm
29 requiring intensive treatment in an emergency room or convulsions that do not
30 result in inpatient hospitalization.

31

32 • Any monitored lab value meeting the Grade 3 or Grade 4 toxicity criteria

33

34 **Bacteremia:** Any episode of bacteremia due to *Lactobacillus reuteri*, the study probiotic,
35 will be considered a Serious Adverse Event. Subjects started on probiotic/placebo

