36 therapy will be monitored for adverse events during the 5 days of probiotic therapy and at
37 2-5 day intervals (when symptoms are recorded and stools are collected) following
38 discontinuation of therapy. Temperature will be documented daily while receiving study
39 intervention and at follow-up visits which include AE monitoring, and participants with new
40 onset of fever following initiation of intervention therapy and participants who appear
41 especially ill or toxic to the field worker will have a physician evaluation. Subjects will also
42 be instructed to present to study personnel for evaluation whenever they suspect they are
43 febrile or a new febrile episode is documented. In cases where fever is grade 3 or 4, or
44 when the subject appears particularly ill or toxic in the estimation of the field worker or

1 physician, blood will be examined in for malaria parasites by thick smear (a standard daily
2 diagnostic procedure in our laboratory) within 8 hours of collection, and antimalarial
3 treatment provided by the Ministry of Health will be administered to subjects with fever and
4 parasitemia. Subjects evaluated in this manner will have a blood culture specimen taken
5 and close monitoring. Presumptive medical therapy will be started at the discretion of the
6 study physician. In the event of positive blood cultures, presumptive antibiotic treatment
7 and hospitalization (if deemed necessary by the attending physician) will be facilitated by
8 project personnel (including procurement). Antibiotic therapy will be the standard pediatric
9 doses of Ceftriaxone and gentamicin for presumed or confirmed common causes of
10 sepsis in this population (*E. coli*, *S. pneumonia*) and clindamycin will be used if study
11 product associated bacteremia is suspected (no source of lower respiratory infection,
12 urinary tract infection, or diarrheal illness noted) or supported by microbiologic data (gram
13 positive rods on initial gram stain).

14

15 **Documenting SAEs**

16 Any AE and SAE occurring during the study must be documented in the SAE CRF and on
17 form FDA 3500 MedWatch. A separate MedWatch form should be used for each SAE.
18 However, if at the time of initial reporting, multiple SAEs are present, they may be reported
19 on the same "SAE" page. If a subject dies during participation in the study or in the 85
20 days following the administration, NIDDK will be provided with a copy of any post-mortem
21 findings, including histopathology.

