22

23 **Post-study AEs and SAEs**

24 Investigators will not actively seek AEs or SAEs in study participants beyond day 28.
25 However, if the investigator learns of any AE at any time after active surveillance ends on
26 day 28 or a subject has completed the study at 3 months, and such event(s) is (are)
27 reasonably related to the study participation, the investigator will promptly notify NIDDK
28 and document the event in as much detail as can be ascertained.

29

30

31 **9.2.3 Unanticipated Problems**

32

33 The Office for Human Research Protections (OHRP) Common Rule 45 CFR §46.103
34 considers unanticipated problems involving risks to subjects or others to include, in
35 general, any incident, experience, or outcome that meets **all** of the following criteria:

- 36 • unexpected (in terms of nature, severity, or frequency) given (a) the research
37 procedures that are described in the protocol-related documents, such as the IRB-
38 approved research protocol and informed consent document; and (b) the
39 characteristics of the subject population being studied;
- 40 • related or possibly related to participation in the research (in the guidance document,
41 possibly related means there is a reasonable possibility that the incident, experience,
42 or outcome may have been caused by the procedures involved in the research); and
- 43 • suggests that the research places subjects or others at a greater risk of harm
44 (including physical, psychological, economic, or social harm) than was previously
45 known or recognized.

An incident, experience, or outcome that meets any of the three criteria above may warrant consideration of substantive changes in the trial in order to protect the safety, welfare, or rights of subjects or others. Examples of corrective actions or substantive changes that might need to be considered in response to an unanticipated problem include:

- changes to the research protocol initiated by the investigator prior to obtaining IRB approval to eliminate apparent immediate hazards to subjects
- modification of inclusion or exclusion criteria to mitigate the newly identified risks
- implementation of additional procedures for monitoring subjects
- suspension of enrollment of new subjects
- suspension of research procedures in currently enrolled subjects
- modification of informed consent documents to include a description of newly recognized risks

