18 receiving the report from the reference laboratory, and values will be recorded on the
19 appropriate CRF (FORM FOR EVALUATION OF LABORATORY VALUES). Abnormal
20 values meeting toxicity level 1 or 2 which do not warrant further clinical investigation will
21 be noted as such on the laboratory values CRF along with an assessment of
22 relationship to the study product. These abnormal values will be reported to the
23 oversight agencies as AEs according to procedures described below. Abnormal
24 values meeting toxicity level 1 or 2 which may, in the judgment of the study physician,
25 warrant further investigation will result in a clinic visit for full evaluation recorded on the
26 ADVERSE EVENT CRF and will be followed to completion and resolution as with other
27 AEs. Abnormal values meeting toxicity levels 3 or 4 will be considered SAEs and will
28 be evaluated, monitored, and reported according to procedures described for SAEs.

29

30 **Documenting AEs**

31 Any AE occurring during the study must be documented in the subject's medical records
32 and on the appropriate AE CRF, i.e. the AE Report Form. Information to be collected on
33 the AE Report Form includes event description, time of onset, investigator assessment of
34 severity, and relationship to the study product, time of resolution of the event, seriousness,
35 and outcome. All adverse events occurring during the study must be documented
36 appropriately regardless to the relationship of the event with study participation.

37

38 The investigator or study physician should attempt to establish a diagnosis of the event
39 based on signs, symptoms, and/or other clinical information. A diagnosis, if known, or
40 clinical signs and symptoms if diagnosis is unknown, rather than the clinically significant
41 abnormal laboratory finding, should be completed on AE CRF form. If no diagnosis is
42 known and clinical signs and symptoms are not present, then the abnormal finding should
43 be recorded. The laboratory data should either be recorded on the AE forms with the
44 reference range and baseline value(s) or copies of the laboratory reports and reference
45 ranges should be sent with the CRF pages.

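### Section 9.2.2 ends active AE and SAE seeking at day 28 and ties later documentation to relatedness, against the plan's own 90-day rule of recording every event whatever its relationship

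*Combined protocol and SAP*

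**What the plan says.** **The restrictive text.** Section 9.2.2, under Post-study AEs and SAEs, states "Investigators will not actively seek AEs or SAEs in study participants beyond day 28". The next sentence deals with events learned of after active surveillance stops at day 28, or after the child completes the study at 3 months. If such an event is "reasonably related to the study participation, the investigator will promptly notify NIDDK" and documents it in detail.

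**The 90-day text.** The Protocol Summary states the primary objective: "Safety will be assessed through the evaluation of adverse effects in both study arms for 90 days following product administration". Day 28 belongs to a different component: "Tolerability will be assessed based on parental report of subjective symptoms of well-being during product administration and thru D28 of the study". Section 9.2.1 requires that AEs on product or within "90 days of follow-up must be documented appropriately regardless of relationship to the" study product. Of the relatedness assessment, 9.2.1 says it is part of "the documentation process, but it is not a factor in determining what is or is not reported". Within 9.2.2 itself, under Documenting SAEs: "Any AE and SAE occurring during the study must be documented in the SAE CRF and on" a MedWatch form. Section 9.2.4 says that all AEs during the study must be documented "appropriately regardless to the relationship of the event with study participation". Section 9.3.1 has deaths and other SAEs reported within 24 hours whether or not they are related.

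**The 3-month contact.** In 7.5B, staff contact parents at 3 months to record new AEs and SAEs, with no relatedness condition. The AE row of the Appendix A grid is marked at day 90.

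**The concern.** Safety over 90 days is the primary objective, and the plan gives two sets of instructions for days 29-90. Staff following 9.2.2 would not ask about events after day 28, and could record only those they judge reasonably related. Staff following 7.5B, 9.2.1, 9.2.4 and Appendix A would ask at 3 months and record everything. The first set yields fewer recorded events, selected by a causality judgement that the rest of the plan keeps out of recording.

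The halting rule in 9.5 is also exposed. It counts similar SAEs whose relationship to product cannot be excluded on review by the study physician and medical monitor. If an SAE after day 28 first had to pass a reasonably-related test, a differently worded judgement would stand ahead of that review.

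The grading conflict matters because 11.1 gives the DSMB a table of all treatment-emergent AEs by intensity and counts each child once per AE at the worst intensity. An event without a grade has no place in that table.

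**Working it through.** The plan has no figure to reproduce here; the check is a comparison of texts.

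**1. Instructions for days 29-90**

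| Place | Are AEs sought or collected? | Does relatedness limit recording? |
|---|---|---|
| 9.2.2, Post-study AEs and SAEs | Not actively | Yes, as worded |
| Protocol Summary, Objectives | Safety assessed for 90 days | No condition stated |
| 7.5B | Yes, at 3 months | No condition stated |
| Appendix A grid and text | Yes, marked at day 90; safety data sought at days 36 and 90 | No condition stated |
| 9.2.1 | All AEs documented within 90 days | No, explicitly |
| 9.2.2, SAE definition | Death criterion refers to 3 months of surveillance | No condition stated |
| 9.2.2, Documenting SAEs | All AEs and SAEs during the study documented | No condition stated |
| 9.2.4 | All AEs during the study documented | No, explicitly |
| 9.3.1 | SAEs reported within 24 hours | No, explicitly |

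**2. Does the Post-study heading remove the conflict?** No. The sentence names day 28 and completion at 3 months as two separate points, so it reaches the interval between them, which lies inside the study.

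**3. What late capture exists?** Parents are told to report fever (7.5B), unscheduled visits go on an AE form (7.8), a child with an SAE stays under safety monitoring for the 3-month follow-up (7.4), and parents are contacted at 3 months (7.5B). Data after day 28 are therefore not absent; the instruction for collecting them conflicts.

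**4. Size.** The documents give no AE rate, so the number of events affected cannot be computed. For scale only: 60 children at 2:1 are 40 and 20, so one affected child left out of a count moves an arm's percentage by 1/40 = 2.5 points or 1/20 = 5.0 points. That holds for any missed child and is not an estimate of this defect.

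**5. Day 36.** The grid marks AE collection on days 1-5, 8, 12, 15, 18, 24 and 28 (11 contacts) and on day 90, but not on day 36. With day 36 the contacts number 11 + 1 + 1 = 13, the total given in 7.5B, so day 36 is a planned contact. The text above the grid speaks of safety information at day 36, 9.2.1 has AEs asked about at every visit, and 7.5A runs intense AE monitoring to day 36. The blank disagrees with all three.

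**6. Severity.** Sections 7.4 and 9.2.1 say unlisted AEs are reported without a severity grade. The next paragraph of 9.2.1 supplies Levels 1-4 for exactly those events, 9.2.4 puts severity on the AE form, and 11.1 tabulates by intensity. Appendix B adds a second general scale, Grades 1-4, with different definitions. Level 4 in 9.2.1 is life-threatening only, whereas Grade 4 in Appendix B also includes inability to manage basic self-care.

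**7. Section 7.5A.** It places the first dose on day 0, sets a 6-week diary, and describes a first-28-days period that ends on day 36. Section 7.4 and Appendix A dose on days 1-5, Appendix A collects the diary on day 28, and section 4 speaks of 28-day diary cards.

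**The case against.** The strongest reply is that the relatedness filter is partly inferred. Section 9.2.2 says what to do when a late event is reasonably related; it does not say that unrelated events go unrecorded, and the rules in 9.2.1 and 9.2.4 are mandatory. On that view, relatedness triggers only prompt notification to NIDDK, and not seeking events actively merely describes the passive phase before the 3-month contact. This reading is possible and may be what was meant. It is not what the sentence says: notification and documentation hang on the same condition, and the first sentence makes no exception for the 3-month contact.

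Other text could also settle the matter. The DSMP and the MOP are separate documents, and the text between 9.2.4 and 9.3.1 was not available here. Any clarification there should be checked, but it would not make the wording of 9.2.2 consistent with the sections set out above.

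A reader might infer that safety data are lost for 62 of the 90 days (90 - 28). The documents do not support that. That figure describes visit spacing, which is a design feature, and the late capture routes above operate in that period. A reader might also infer bias between the arms. The same instruction applies to both arms, and field staff and physicians are masked, so the documents give no ground for expecting the loss to differ by arm.

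On grading, it is fair to say that 9.2.1, 9.2.4 and 11.1 together point towards grading unlisted AEs. That makes the no-grading sentences easy to remove, but two rival general scales would remain.

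**Conclusion.** The conflict is real and should be fixed. As written, 9.2.2 contradicts the plan's 90-day, relationship-blind recording rule and its 3-month AE contact. The consequence is a risk of under-recording the primary safety outcome in days 29-90, in both masked arms. How many events are at risk cannot be stated from the documents. It depends on an AE rate they do not give and on which instruction staff follow. The conclusion rests on reading the 9.2.2 sentence as it stands, with documentation under the relatedness condition. Even on the narrower reading, the sentence about not actively seeking events still disagrees with 7.5B and Appendix A.

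The day-36 blank, the grading contradiction with its two scales, and the numbering and diary length in 7.5A are smaller drafting inconsistencies in the same AE instructions.

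**What to change.** 1. In 9.2.2, Post-study AEs and SAEs, change the limit in the first sentence from day 28 to the 3-month contact. In the second sentence, delete the clause naming day 28 as the end of active surveillance. The relatedness condition then applies only after study completion, and all AEs and SAEs up to then are documented whatever their relationship.
2. Mark AE collection at day 36 in the Appendix A grid, to agree with its own text, 9.2.1 and 7.5A.
3. Delete the sentences in 7.4 and 9.2.1 that leave unlisted AEs ungraded. Reconcile Levels 1-4 in 9.2.1 with the general Grades 1-4 in Appendix B, so that one scale applies to unlisted AEs and feeds the by-intensity table in 11.1.
4. Reconcile 7.5A with 7.4 and Appendix A on the day number of the first dose, and with section 4 and Appendix A on the length of the diary. Also reconcile its 28-day label with its day-36 end. The documents do not show which version is intended, and this point does not presume one.

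The cost is protocol wording and one mark at an existing visit. No visit, sample or new scale is added. The DSMP and MOP should be checked for matching wording.

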9.3.1 Serious Adverse Events

Any AE considered serious by the study physician or which meets the aforementioned criteria must be submitted on a SAE form to the appropriate IRBs, INS, DSMB designate and the NIDDK. The SAE form will be sent as an email attachment or fax to each relevant institutional representative within the time frame below:

* All deaths, whether related or unrelated, will be recorded on the Serious Event Form and on MedWATCH FDA 3500 (2/13) and sent by fax and email within 24 hours of the site awareness of the death.

* Serious adverse events other than death, regardless of relationship, will be reported via fax and email by the site within 24 hours of becoming aware of the event.

Other supporting documentation of the event may be provided upon request as soon as possible.

All serious adverse events will be:

- recorded on the appropriate serious event case report form
- followed through resolution by a study physician
- reviewed by a study physician

All SAEs will be followed until satisfactory resolution of the event or until the study physician deems the event to be chronic or the patient to be stable.

1 The investigator, or responsible person according to local requirements, must comply with
2 the applicable local regulatory requirements related to the reporting of SAEs to regulatory
3 authorities and the IRB/EC.

4
5 **SAEs will be reported to the institutional representatives at the fax and email**
6 **addresses shown in the section entitled Reporting of Adverse Events.**

7
8
9
10 **9.3.2 Regulatory Reporting for Studies Not Conducted Under**
11 **NIDDK-Sponsored IND**

12
13 Procedures for reporting AEs and SAEs are described in the corresponding sections on
14 AE and SAE reporting.

15
16
17 **9.4 Type and Duration of Follow-up of Subjects after Adverse**
18 **Events**

19
20 **Follow-up of AEs**
21 All AEs will be followed until resolution, until the condition stabilizes, until the event is
22 otherwise explained, or the subject is lost to follow-up. The ADVERSE EVENT CRF
23 includes space for up to two follow-up visits for the same AE. The investigators will
24 ensure that follow-up includes any supplemental investigations as may be indicated to
25 elucidate as completely as practical the nature and/or causality of the AE. This may
26 include additional laboratory tests or investigations, histopathological examinations, or
27 consultation with other health care professionals. New or updated information should be
28 recorded on the originally completed AE CRF with all changes signed and dated by the
29 investigator.

30
31 **9.5 Halting Rules**

32
33 The study will be halted if two or more individuals develop similar SAEs for which a
34 relationship to the study product cannot be excluded upon study physician and medical
35 monitor review. Participants who develop an SAE, regardless of cause, will discontinue
36 the study treatment if treatment is still ongoing.

37
38 Subsequent review of serious, unexpected, and related AEs by the Medical Monitor,
39 IRB, or NIDDK may also result in suspension of further administration of study product.
40 NIDDK, typically in conjunction with DSMB recommendations, retains the authority to
41 suspend additional enrollment and study interventions/administration of study product
42 for the entire study, as applicable.

43
44 Examples of findings that might trigger a safety review are the number of SAEs overall

1 and by treatment group during the closed DSMB sessions, the number of occurrences
2 of a particular type of SAE, severe AEs/reactions, or increased frequency of events.

3

4 **9.6 Safety Oversight**

5

6 Safety oversight for this Phase 1 study Safety of *Lactobacillus reuteri* in healthy children
7 aged 2-24 months is outlined in the attached Data and Safety Monitoring Plan. A medical
8 monitor has been contracted to evaluate AE reporting and they and NIDDK staff and study
9 staff will review open reports that do not specify treatment group when adverse events
10 and out of range values are summarized on a quarterly basis. Additionally, an NIDDK
11 appointed DSMB will monitor safety data by treatment group for this Phase 1 study by
12 examining a closed report in which out of range laboratory values and adverse events are
13 reported by treatment group on a quarterly basis. This closed report will be prepared
14 based on the final open report. Our project biostatistician (unmasked) will communicate
15 with the project biostatistician who is not involved in any data entry or cleaning of the data
16 while the trial is ongoing and transfer the data and treatment assignment by PID to the
17 biostatistician to elaborate the same tables as those present in the DSMP, but with
18 treatment assignment. This will be reviewed by unblinded members of the NIDDK as well
19 as the DSMB.

20

21

22

7
8
9
10 **10 CLINICAL MONITORING**

11
12 Clinical monitoring will be carried out in two ways:

13
14
15
16
17
18 1. The investigators have outlined a detailed Data and Safety Monitoring Plan,
19 described in a separate DSMP document. The clinical and statistical monitors
20 performing this function are listed in section 9.6 Safety Oversight. Procedures for
21 and frequency of this clinical monitoring are described in the DSMP.

22
23 2. NIDDK will provide regulatory and compliance monitoring through an NIDDK-
24 appointed site monitor, contracted through a certified research monitoring agency
25 such as Westat. Frequency and scope of this oversight will be determined by
26 NIDDK.

27
28
29
30 **10.1 Site Monitoring Plan**

31
32 Site monitoring is conducted to ensure that the human subject protection, study
33 procedures, laboratory, study intervention administration, and data collection processes
34 are of high quality and meet the sponsor, ICH E6 and, when appropriate, regulatory
35 guidelines.

